7.3 Environmental exposure measurement

Exposure assessment of PM_{2.5} is measured based on the daily activity pattern of students, including indoor measurement (residence and classroom) and ambient measurement during their commute to school. Indoor PM_{2.5} exposure data is collected by installing Hike B3-L2 (Beijing Haike Zhidong Technology Development Co. LTD, China) in the study children's bedrooms and classrooms. The monitors are installed on a platform at least 1m from the purifier and approximately 1.5m above the floor. The monitors collect ambient PM_{2.5} concentrations every five minutes, and we collect real-time PM_{2.5}

exposure levels in bedrooms and classrooms for the duration of the study. Secondly, real-time outdoor PM_{2.5} data is collected by installing a micro atmospheric environment monitoring station (Capri Environmental Technology Ltd., Shenzhen, Guangzhou) on the roof of the school. Meanwhile, this micro atmospheric environment monitoring station also monitors and collects outdoor concentrations of PM₁₀ (µg/m³), NO₂ (µg/m³), SO₂ (µg/m³), CO (mg/m³), and O₃ (µg/m³). Finally, twenty-four-hour time-weighted mean PM_{2.5} concentrations are calculated as personal daily exposures based on PM_{2.5} concentrations in different environments and twenty-four-hour time-activity patterns of survey respondents. The monitoring particle concentration data has undergone quality control and calibration following the previous approach ². Temperature and relative humidity are collected via the HOBO® MX Temp/RH Data Logger MX1101 (Onset, USA).

7.4 Questionnaire

The questionnaire is in the form of an electronic questionnaire (questionnaire.com). Professional staff train and qualify classroom teachers to supervise parents and students to complete the parent questionnaire, student questionnaire and the 24h time-activity questionnaire. Information collected during the baseline survey does not have to be collected for the other surveys if there is no significant change during the other surveys.

The parent questionnaires are conducted on the parents of the students, and the survey included basic family information, living environment, risk perception, and child evaluation scale (parent volume). The children's questionnaires are conducted on students, and the survey included risk perceptions and the Children's Evaluation Scale (Children's Volume). The 24h time-activity questionnaires are conducted on students, documenting their activity patterns and diet behaviors.

7.5 Physical Examination

7.5.1 Height measurement

Height measurement is conducted by using a tape measure fixed on the wall. Before the measurement, the subjects are required to take off their shoes, hats and outerwear, stand on the pedal and maintain an upright posture. After the measurement is completed, the accurate measurement results are filled into the physical examination form.

7.5.2 Weight measurement

Weight measurement is performed using an electronic weight scale. Measurements are taken in a quiet, spacious environment with a level and firm floor. After the measurement is completed, the results are entered into the medical examination form in a timely manner.

7.5.3 Waist circumference measurement

Waist circumference is measured using a waist tape. The subject stands upright, with the abdomen relaxed, arms hanging down naturally, feet combined and weighted evenly, exposing the abdominal skin. After completing the measurement, the results are entered into the physical examination form.

7.5.4 Hip circumference measurement

Hip circumference measurement is performed using a waist circumference tape. The soft ruler is lightly pressed against the skin, passing through the highest point of the buttocks and circling around the body. Measurements are carried out twice, with a difference of no more than 1 cm, and the average value should be recorded in the physical examination form.

7.6 Respiratory health measurements

Pulmonary function measures are performed by a professional medical device. Before the pulmonary function test, subjects practiced several times with the guidance of professional staff. During the examination, each subject is in a sitting position clamp the nose clip, and repeat the test, with the best

result as the criterion. The indicators include FEV₁, FVC, FEV₁/FVC, PEF, FEF_{25-75%}, MEF_{75%}, MEF_{50%}, MEF_{25%}. A NIOX VERO Sensor is used to measure fractional exhaled nitric oxide (FeNO) as a biomarker for airway inflammation. After deep breathing, the subjects gently inhaled into the device. The instrument shows the FeNO level of the subjects. Use PICO to measure fractional exhaled carbon monoxide (FeCO) as a biomarker. After deep breathing and holding the breath for 15 seconds, the subjects gently inhaled into the device. The instrument shows the FeCO and COHb level of the subjects.

7.7 Blood pressure measurement

After a 5-minute rest in a quiet environment, the child-appropriate BP cuff is wrapped around the left upper arm of the children to measure BP using the Omron electronic sphygmomanometers (OMROM, J751). BP is measured at 2-minute intervals, with a total of three measurements taken. If the difference in BP values between the last two measurements exceeds 5 mmHg, additional measurements are performed. Each child is allowed to measure BP at least three times and up to five times. The SBP, DBP and heart rate are recorded; the mean arterial pressure (MAP) and pulse pressure (PP) are calculated. The HOBO thermo-hygrometer is set up in the medical examination room to monitor the temperature and relative humidity.

7.8 Heart rate variability measurements

A 3-minute comprehensive assessment is conducted to measure HRV using the handheld electrocardiographic recorder-CarePatch (ECG-H01, Hangzhou Proton Technology Co., Ltd., China). The participants are required to rest quietly for 2 minutes before the measurement. The professional staff activate the Bluetooth on the terminal device (Thinkpad) and enter the “CarePatch” (a WeChat Mini Program), then guide the children to hold the electrodes with their thumbs at moderate pressure for a “3-minute comprehensive examination”. During this process, children are prohibited from speaking or physical activity. 3 time-domain indicators, including standard deviation of all normal-to-normal intervals (SDNN), the root mean square of successive differences between adjacent normal cycles (rMSSD), the percentage of adjacent NN interval differences greater than 50 ms (pNN50); and 4 frequency-domain indicators, including very low frequency (VLF), low frequency (LF), high frequency (HF), the ratio of LF to HF (LF/HF) are selected.

7.9 Electrocardiograph measurements

The staff use a 12-lead electrocardiogram (ECG) to record the values of PR interval (the interval of the beginning of the P wave to the beginning of the QRS complex), QRS duration (the interval of the beginning of Q wave to the end of the S wave), QT interval (the interval from the onset of the QRS complex to the end of the T wave), QTc interval (the QT correction for rate), RV5 (amplitude of the R wave in lead V5), SV1 (S-wave depth in lead V1), and RV5+SV1 (the sum of the R-wave amplitude in lead V5 and the S-wave amplitude in lead V1).

7.10 Academic achievement measurements

Academic achievement is collected at the beginning and end of each study period. The evaluation of academic performance consisted of standardized scores (maths, chinese and total) and the relative ranking of the scores within the grade. Standardized grades are converted from raw grades by z-scores according to the number of exams and class in order to eliminate differences due to different exams; rankings are converted from place rankings of raw grades, reflecting the relative value of grades.

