3.2 Primary and Secondary Outcomes

The primary outcomes for respiratory health are lung function indicators, including forced expiratory volume in 1 s (FEV₁), forced vital capacity (FVC), FEV₁/FVC ratio, peak expiratory flow (PEF), forced expiratory flow at 25–75% of FVC (FEF_{25-75%}), maximal expiratory flow at 75% of FVC (MEF_{75%}), maximal expiratory flow at 50% of FVC (MEF_{50%}), and maximal expiratory flow at 25% of FVC (MEF_{25%}); changes of FeNO; Changes of FeCO. The primary outcomes for cardiovascular health are blood pressure indicators, including systolic blood pressure (SBP), diastolic blood pressure (DBP), mean arterial pressure (MAP) and pulse pressure (PP); heart rate variability indicators, including standard deviation of all normal-to-normal intervals (SDNN), the root mean square of successive differences between adjacent normal cycles (rMSSD), the percentage of adjacent NN interval differences greater than 50 ms (pNN50), very low frequency (VLF), low frequency (LF), high frequency (HF), the ratio of LF to HF (LF/HF); and electrocardiograph parameters, including the interval of the beginning of the P wave to the beginning of the QRS complex (PR interval), the interval of the beginning of Q wave to the end of the S wave (QRS duration), the interval from the onset of the QRS complex to the end of the T wave (QT interval), the QT correction for rate (QTc interval), amplitude of the R wave in lead V5 (RV5), S-wave depth in lead V1 (SV1) and the sum of the R-wave amplitude in lead V5 and the S-wave amplitude in lead V1 (RV5+SV1). The primary outcomes for cognitive health are academic performances, including standardized scores and relative ranking of scores.

The secondary outcomes include the metabolites in exhaled breath condensate, serum protein, the indicators measured by the Wisconsin Card Sorting Test, Attention Network Test, and N-BACK Test. Furthermore, other omics and targeted biomarkers of interest (e.g., CRP, 8-OHdG, etc) are also considered.

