3.3 Stratification, Randomization, and Blinding

Students are allocated by class cluster randomization to the intervention group or the control group. The intervention assignment is handed over to independent trained professionals, who do not participate in

any other processes of the trial. Confidentiality of the intervention is maintained for the researcher and participants to achieve double blindness.

4. Participants and Sites

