6.1 Intervention

The intervention group is equipped with purifiers with true-purification (i.e., with high-efficiency particulate air (HEPA) filter), and the control group with sham-purification purifiers (without HEPA filter), which are installed in the classrooms and households of both groups. In the school environment, an air purification efficiency of 850 m³/h (LEXY, KJ901) and a fresh air ventilation with the purification efficiency of 320 m³/h (AIRTAO, AT320) are placed in the front of the classroom and the air purification equipment is the same as the back of classroom. In the home environment, one air purifier with the purification efficiency of 220 m³/h (Haier, KJ210F-A180A) is installed in each of the children's bedroom. Two different treatments are employed, including true-purification and sham-purification, in random order with a washout period of over 2 months. The air purification intervention is performed by trained professionals on and off at regular intervals each day to ensure that the air purification unit is on during the time the children are in the indoor environment. In the event of offline situations such as those caused by poor internet access, the survey respondents are contacted and communicated with promptly. A health examination is conducted at the beginning and end of each study period, and a questionnaire is used to collect basic information about the respondents. We also measured the environmental factors including

PM_{2.5} concentration, temperature, and relative humidity. 24 time-weighted mean PM_{2.5} concentrations are calculated as personal daily exposures for further analysis.

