8.1 Sample size calculation

In this randomized, double-blind crossover study, the sample size is determined according to the relative literature on respiratory outcome⁶⁻⁸, cardiovascular outcome⁹⁻¹⁰, and cognitive function outcome¹¹ and confirmed in PASS15.0 software with the statistical significance of 0.05. Combined with the supporting

evidence and the requirement of sample size calculated in PASS15.0, and considering the typical number of students in each class and the possible withdrawal, we ultimately plan to recruit 100 children for this study.

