8.2 Analytical models

We use a linear mixed-effects model to estimate the effects of air purification intervention or per interquartile range (IQR) decrease in personal PM_{2.5} exposure on several functional indicators and targeted biomarkers of children's health. To account for the impact of varied outcome levels at baseline, the absolute or relative change in outcome level is calculated as the difference between post-intervention and pre-intervention, comparing the change in health outcomes between the intervention and control groups after the intervention. We further adjusted for the confounders including sex, age, body mass index (BMI, kg/m²), temperature (°C), relative humidity (%), etc. A random intercept for each participant is included in the models to account for the repeated measurements.

In addition, we plan to perform metabolomics analysis of EBC samples using ultra-high performance liquid chromatography-tandem mass spectrometry and proteomic analysis of serum samples with 4D-label free technology. Besides, other omics analyses and targeted biomarkers of interest are planned to further explore the potential biological mechanisms.

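### If the z-scores in 7.10 are taken within school class, the standardised academic scores are centred within the randomised unit and a class-wide treatment effect cancels

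*Combined protocol and SAP*

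**What the plan says.** All references are to the combined protocol and SAP.

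- **Scaling (7.10).** Standardised maths, Chinese and total scores are "converted from raw grades by z-scores according to the number of exams and class in order to eliminate differences due to different exams". The second academic measure is a rank within the grade, derived from the raw marks.
- **Status (3.2).** "The primary outcomes for cognitive health are academic performances, including standardized scores and relative ranking of scores".
- **Randomised unit (3.3, repeated in 7.2).** "Students are allocated by class cluster randomization to the intervention group or the control group". Section 8.1 uses the word in the same sense: "considering the typical number of students in each class".
- **Delivery (6.1).** The school devices serve the whole room: they "are placed in the front of the classroom and the air purification equipment is the same as the back of classroom". Each enrolled child also has a bedroom device.
- **Analysis (8.2).** "the absolute or relative change in outcome level is calculated as the difference between post-intervention and pre-intervention". The model has a random intercept for each participant, and the stated approach is "comparing the change in health outcomes between the intervention and control groups after the intervention".

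The plan names a grouping (exam and class). It does not say which children supply the mean and SD, or define 'class' in this sentence.

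**The concern.** A z-score removes the mean of its reference group. If that group is one school class at one exam, it is also the unit that was randomised, and every analysed child in it has the same treatment. Any gain that purification gives to the class as a whole raises each child's mark and the class mean together, so the z-scores do not move. The between-group comparison in 8.2 cannot restore what the scaling has removed. The crossover does not help either, because each class is re-centred at every exam in both periods.

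The standardised scores would then show a treatment estimate near 0 with an ordinary-looking standard error, and a reader could take that as evidence of no effect. The within-grade rank could show an effect at the same time, and the two academic measures would disagree only because of how one of them was scaled.

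**Working it through.** There is no figure in the plan to reproduce. Section 8.1 gives a planned 100 children (the synopsis gives 105), but no effect size, SD or power, and no number of classes or enrolled share. The identities in steps 1 to 3 need none of these; the illustrations do.

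**1. Analysed children as the reference set.** For child *i*, class *k*, exam *t*:

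z_ikt = (y_ikt − ȳ_kt) / s_kt

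Add a shift *d* to everyone in class *k*. Then (y + d) − (ȳ + d) = y − ȳ, and s is unchanged, so z is unchanged. The same holds for a proportional gain a·y + d with a > 0. The mean of z in each class is 0 at every exam, so the mean change is 0 in each class and period, and the true-minus-sham contrast is 0 − 0 = 0.

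**2. Whole class as the reference set, enrolled share f.** Let the classroom effect be *c* and the home effect, in enrolled children only, be *h*. An enrolled child shifts by c + h and the class mean by c + f·h. The difference is (1 − f)·h. The classroom effect has gone, and about (1 − f) of the home effect is left.

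**3. Reference set across classes.** The mean and SD at an exam are then common to both groups. Subtracting the same mean from both leaves the difference between them in place, divided by the pooled SD.

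**4. Numerical check.** Assumed: two classes of 50 or four of 25, raw SD about 10 points, true effect +3 points (about 0.3 SD), four exams, post-minus-pre change in a two-period class crossover, 4,000 runs per row.

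| Reference set | Mean estimate (SD units) |
|---|---|
| School class, all analysed, +3 points | 0.0000 (largest absolute value below 1e-14) |
| Same, 10% proportional gain plus 3 points | 0.0000 |
| School class, 25 of 50 enrolled, class-wide effect | −0.001 |
| School class, 25 of 50 enrolled, home-only effect | 0.147; formula (1 − 0.5) × 0.3 = 0.15 |
| School class, 40 of 50 enrolled, home-only effect | 0.060; formula (1 − 0.8) × 0.3 = 0.06 |
| Across the grade, 2 × 50 | 0.282 |
| Across the grade, 4 × 25 | 0.281 |

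The across-grade figures fall slightly below 0.30 because the pooled SD includes class differences and the effect itself.

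**5. Mixed model.** A random-intercept model with treatment, period, BMI, sex and age was fitted to 40 data sets. With class-centred scores the estimate is 0 to rounding, with mean SE 0.1196, so a 95% interval of about ±1.96 × 0.1196 = ±0.23. That interval would exclude the assumed 0.3 SD effect. With across-grade scores the mean estimate is 0.275.

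**6. Other assumed effects.** For true effects of 0.2, 0.5 and 0.8 SD (class SD 0.2, within-child correlation 0.7), class-centred scores give 0.00 each time. Across-grade scores give 0.19–0.20, 0.47–0.48 and 0.72–0.75.

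**7. Departures from complete data.** With a true effect of 0.5 SD, adding temperature and humidity to the covariates gives class-centred estimates with mean 0.00 and SD 0.01. With 10% of changes missing the SD is 0.04. The estimate is then no longer exactly 0, but it carries no class-wide signal.

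**The case against.** The strongest reply is that everything turns on one word in a loosely written sentence. The stated purpose concerns exams only, and the preceding sentence lists subjects, so 'exam by subject' is a live reading. The fact that class centring does not serve the stated purpose is itself some evidence that it was not meant. Nor does it settle the matter that 7.10 calls the year group the grade, because it also uses 'grade' for a mark. This stands: the school-class reading is the plainest, since 3.3, 7.2 and 8.1 use the word that way, but it is not established. If 'class' means subject or year group and the reference set spans both groups, there is no cancellation.

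A second reply is that centring by class may have been needed. If the classes sat different papers, or were marked differently, across-class z-scores would carry exam difficulty into the group contrast. The within-grade ranking suggests a common exam, but nothing says so. This also stands, and the fix has to be conditional on it.

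A reader might go further and infer that the academic domain as a whole cannot show an effect. The documents do not support that: the rank is taken across the grade from raw marks and is not centred by class. A reader might also put a figure on the damage to the analysis "per interquartile range (IQR) decrease in personal" PM2.5, or to relative change. The exposure spread that the first would need is not given, and 8.2 offers relative change for outcomes in general without assigning it to z-scores. Neither is relied on here.

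**Conclusion.** The point holds as a conditional one and should be fixed. Section 7.10 leaves the reference set open, and on its plainest reading one of the two academic primary measures cannot register a treatment effect shared by a class. In that case the absolute-change contrast is exactly 0 for complete data with the analysed children as reference; with non-enrolled classmates included, only about (1 − f) of a home-only effect remains.

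This identity depends on no assumed effect size, class count or SD. The illustration of 0 against about 0.28 SD does. A reader might infer that the plan is shown to be wrong, or that the scores have in fact been centred by class. The text is too ambiguous for either. What it shows is that a null result on this measure could not be interpreted without knowing which reading was applied. The respiratory and cardiovascular primary outcomes are not touched.

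**What to change.** In 7.10, state that z-scores are computed per subject (maths, Chinese, total) and per exam, across all classes in the grade that sat that same exam, and not within class. If marks for the whole grade are not held, use all enrolled children who sat that same exam. Either way, both groups must be in every reference set. If 'class' was meant as something other than the school class, correct the sentence to say so.

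If the classes sat different exams, say so, and do not interpret the within-class z-score contrast as a test of a class-wide effect.

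The cost is a sentence or two in 7.10 and a recalculation from the raw marks. The documents do not show that whole-grade marks are held, but the conversion starts from raw marks, so the version using enrolled children should be feasible if they sat a common exam. There are two downsides:

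- Between-class variation returns to the outcome, so the intervals must allow for class.
- The trial period was April to December 2021 and the document is dated 12 September 2024, so the marks should already have been collected. The scaling should be settled before unblinded analysis, or reported as changed afterwards with results on the scaling in the present text shown alongside. The documents do not say whether unblinded analysis has taken place.

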7.11 Cognitive executive function measurements

7.11.1 The Attention Network Test

The Attention Network Test (ANT) is used to measure an individual's ability to acquire and maintain a state of alertness to a certain type of information or target, selective attention to externally useful

information, and processing of conflicting information. The ANT is a computer-based, annotated test that is typically used to measure different behavioral aspects of attention, and it is based on the Attention Network Theory.

The ANT is divided into two phases: a practice and a formal game. The practice phase consists of 10 questions that are used to familiarize with the operation. After completing the exercise, the system prompts the start of the formal game. The formal game is divided into three parts, with the option of resting or continuing directly between each part. In this test, the subject's task is to feed a hungry little fish located right in the middle by judging the direction of its mouth. When the mouth of the small fish is facing left, press the left button; when the mouth of the small fish is facing right, press the right button. During the test, the subject is asked to look intently at the gaze point (+) on the screen as it will indicate where the minnow is likely to appear. Also, watch out for the left and right buttons to show clear positions on the screen.

